### 9.2.1.3 End of Treatment and Follow-up Tumor Imaging

For participants who discontinue study treatment, tumor imaging should be performed at the time of treatment discontinuation (±4 week window). If previous imaging was obtained within 4 weeks prior to the date of discontinuation, then imaging at treatment discontinuation is not mandatory. For participants who discontinue study treatment due to documented disease progression, this is the final required tumor imaging if the investigator elects not to implement iRECIST.

For participants who discontinue study treatment without documented disease progression, every effort should be made to continue monitoring disease status by tumor imaging using the same imaging schedule used while on treatment every 12 weeks (±7 days) until the start of a new anticancer treatment, disease progression, pregnancy, death, withdrawal of consent, or the end of the study, whichever occurs first.

### 9.2.1.4 RECIST 1.1 Assessment of Disease

RECIST 1.1 (assessed by investigator) will be used as the primary measure for assessment of tumor response, date of disease progression, and as a basis for all protocol guidelines related to disease status (eg, discontinuation of study treatment).

MK-7123-034-01 Final Protocol
22-Mar-2018
Confidential

#### 9.2.1.5 iRECIST Assessment of Disease

The iRECIST method is based on RECIST 1.1, but adapted to account for the unique tumor response seen with immunotherapeutic drugs. iRECIST will be used by the Investigator to assess tumor response and progression, and make treatment decisions. When clinically stable, participants should not be discontinued until progression is confirmed by the Investigator, working with local radiology, according to the rules outlined in Appendix 7. This allowance to continue treatment despite initial radiologic PD takes into account the observation that some participants can have a transient tumor flare in the first few months after the start of immunotherapy, and then experience subsequent disease response. This data will be captured in the clinical database.

Clinical stability is defined as the following:

- Absence of symptoms and signs indicating clinically significant progression of disease
- No decline in ECOG performance status
- No requirements for intensified management, including increased analgesia, radiation, or other palliative care

Any participant deemed clinically unstable should be discontinued from study treatment at site-assessed first radiologic evidence of PD, and is not required to have repeat tumor imaging for confirmation of PD by iRECIST.

If the Investigator decides to continue treatment, the participant may continue to receive study treatment and the tumor assessment should be repeated 4 to 8 weeks later to confirm PD by iRECIST, per Investigator assessment. Images should continue to be sent in to the central imaging vendor for potential retrospective BICR.

If repeat imaging does not confirm PD per iRECIST, as assessed by the investigator, and the participant continues to be clinically stable, study treatment may continue and follow the regular imaging schedule. If PD is confirmed, participants will be discontinued from study treatment.

[figure not shown]
If a participant has iRECIST confirmed radiographic progression (iCPD) as defined in Appendix 7, study treatment should be discontinued; however, if the participant is achieving a clinically meaningful benefit, an exception to continue study treatment may be considered following consultation with the Sponsor. In this case, if study treatment is continued, tumor imaging should continue to be performed following the intervals as outlined in Section 2 and submitted to the central imaging vendor.

A description of the adaptations and iRECIST process is provided in Appendix 7, with additional details in the iRECIST publication [Seymour, L., et al 2017].

Guidance for imaging and treatment after first radiologic evidence of progressive disease is shown in Table 6 and for clinically stable participants in Figure 3.

Table 6 Imaging and Treatment After First Radiologic Evidence of Progressive Disease

	Clinically Stable		Clinically Unstable		
	Imaging	Treatment	Imaging	Treatment	
First radiologic evidence of PD by RECIST 1.1 that has been verified by BICR]	Repeat imaging at 4 to 8 weeks to confirm PD.	May continue study treatment at the investigator's discretion while awaiting confirmatory tumor imaging by site by iRECIST.	Repeat imaging at 4 to 8 weeks to confirm PD per investigator's discretion only.	Discontinue treatment	
Repeat tumor imaging confirms PD (iCPD) by iRECIST per investigator assessment	No additional imaging required.	Discontinue treatment (exception is possible upon consultation with Sponsor).	No additional imaging required.	Not applicable	
Repeat tumor imaging shows iUPD by iRECIST per investigator assessment	Repeat imaging at 4 to 8 weeks to confirm PD. May occur at next regularly scheduled imaging visit.	Continue study treatment at the investigator's discretion.	Repeat imaging at 4 to 8 weeks to confirm PD per investigator's discretion only.	Discontinue treatment	
Repeat tumor imaging shows iSD, iPR, or iCR by iRECIST per investigator assessment.	Continue regularly scheduled imaging assessments.	Continue study treatment at the investigator's discretion.	Continue regularly scheduled imaging assessments.	May restart study treatment if condition has improved and/or clinically stable per investigator's discretion. Next tumor imaging should occur according to the regular imaging schedule.	

Imaging and Treatment for Clinically Stable Participants Treated With Pembrolizumab After First Radiologic Evidence of PD Assessed by the Investigators

iRECIST=modified Response Evaluation Criteria in Solid Tumors 1.1 for immune-based therapeutics; PD=progressive disease; RECIST 1.1=Response Evaluation Criteria in Solid Tumors 1.1

### 9.2.2 Prostate-Specific Antigen

The initial Prostate-Specific Antigen (PSA) biomarker assessment at screening must be performed within 28 days prior to the date of allocation.

In the first year (through Week 54), on study PSA biomarker assessments must be performed every 9 weeks (63 days  $\pm$ 7 days) from the date of allocation. After one year, participants who remain on-treatment will have PSA performed every 12 weeks (84 days  $\pm$ 7 days).

#### **MSI Status in CPRC Patients**

MSI status will be tested in participants with CRPC who demonstrate an objective response (either confirmed or unconfirmed) to therapy.

MSI status can be evaluated using the archival or newly obtained tumor tissue collected at screening.

#### 9.3 Adverse Events (AE), Serious Adverse Events (SAE) and Other Reportable Safety Events

The definitions of an adverse event (AE) or serious adverse event (SAE), as well as the method of recording, evaluating, and assessing causality of AE and SAE and the procedures for completing and transmitting AE, SAE and other reportable safety event reports can be found in Appendix 4.

Progression of the cancer under study is not considered an adverse event as described in Section 9.3.5 – Disease-Related Events and/or Disease-Related Outcomes Not Qualifying as AEs or SAEs, and Appendix 4.

AE, SAEs, and other reportable safety events will be reported by the participant (or, when appropriate, by a caregiver, surrogate, or the participant's legally authorized representative).

The investigator, who is a qualified physician, and any designees are responsible for detecting, assessing, documenting, and reporting events that meet the definition of an AE or SAE as well as other reportable safety events. Investigators remain responsible for following up AE, SAEs and other reportable safety events for outcome according to Section 9.3.3.

Adverse events will not be collected for participants during the pre-screening period (for determination of archival tissue status) as long as that participant has not undergone any protocol-specified procedure or intervention. If the participant requires a blood draw, fresh tumor biopsy etc., the participant is first required to provide consent to the main study and AEs will be captured according to guidelines for standard AE reporting.

## 9.3.1 Time Period and Frequency for Collecting AE, SAE and Other Reportable **Safety Event Information**

All AEs, SAEs and other reportable safety events that occur after the consent form is signed but before treatment allocation/randomization must be reported by the investigator if the participant is receiving placebo run-in or other run-in treatment, if the event cause the participant to be excluded from the study, or is the result of a protocol-specified intervention, including but not limited to washout or discontinuation of usual therapy, diet, or a procedure.

- All AEs from the time of treatment allocation/randomization through 30 days following cessation of study treatment must be reported by the investigator.
- All AEs meeting serious criteria, from the time of treatment allocation/randomization through 90 days following cessation of study treatment, or 30 days following cessation of study treatment if the participant initiates new anticancer therapy. whichever is earlier must be reported by the investigator.
- All pregnancies and exposure during breastfeeding, from the time of treatment allocation/randomization through 120 days following cessation of study treatment, or 30 days following cessation of study treatment if the participant initiates new anticancer therapy must be reported by the investigator.
- Additionally, any SAE brought to the attention of an investigator at any time outside of the time period specified above must be reported immediately to the Sponsor if the event is considered to be drug-related.

Investigators are not obligated to actively seek AE or SAE or other reportable safety events in former study participants. However, if the investigator learns of any SAE, including a death, at any time after a participant has been discharged from the study, and he/she considers the event to be reasonably related to the study treatment or study participation, the investigator must promptly notify the sponsor.

All initial and follow-up AEs, SAEs and other reportable safety events will be recorded and reported to the sponsor or designee within the timeframes as indicated in Table 7.

Reporting Time Periods and Timeframes for Adverse Events and Other Reportable Safety Events

Type of Event	Reporting Time Period: Consent to Randomization/ Allocation	Reporting Time Period: Randomization/ Allocation through Protocol- Specified Follow-up Period	Reporting Time Period: After the Protocol Specified Follow-up Period	Timeframe to Report Event and Follow-up Information to SPONSOR:
Non-Serious Adverse Event (NSAE)	Report if: - due to protocol- specified intervention - causes exclusion - participant is receiving placebo run-in or other run-in treatment	Report all	Not required	Per data entry guidelines
Serious Adverse Event (SAE) including Cancer and Overdose	Report if: - due to protocol- specified intervention - causes exclusion - participant is receiving placebo run-in or other run-in treatment	Report all	Report if: - drug/vaccine related. (Follow ongoing to outcome)	Within 24 hours of learning of event
Pregnancy/Lactation Exposure	Report if: - due to intervention - causes exclusion	Report all	Previously reported – Follow to completion/termination; report outcome	Within 24 hours of learning of event
Event of Clinical Interest (require regulatory reporting)	Report if: - due to intervention - causes exclusion	Report - Potential DILI - Require regulatory reporting	Not required	Within 24 hours of learning of event
Event of Clinical Interest (Do not require regulatory reporting)	Report if: - due to intervention - causes exclusion	Report - non-DILI ECIs and those not requiring regulatory reporting	Not required	Within 5 calendar days of learning of event

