### 7.2.2 Pembrolizumab Dose Modification

AEs associated with pembrolizumab exposure may represent an immunologic etiology. These immune-related AEs (irAEs) may occur shortly after the first dose or several months after the last dose of pembrolizumab treatment and may affect more than one body system simultaneously. Therefore, early recognition and initiation of treatment is critical to reduce complications. Based on existing clinical study data, most irAEs were reversible and could be managed with interruptions of pembrolizumab, administration of corticosteroids and/or other supportive care. For suspected irAEs, ensure adequate evaluation to confirm etiology or exclude other causes. Additional procedures or tests such as bronchoscopy, endoscopy, skin biopsy may be included as part of the evaluation. Based on the severity of irAEs, withhold or permanently discontinue pembrolizumab and administer corticosteroids. Dose modification and toxicity management guidelines for irAEs associated with pembrolizumab are provided in Table 4

04W5XD

Table 4 Dose Modification and Toxicity Management Guidelines for Immune-related AEs Associated with Pembrolizumab

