### 9.11.3 Post-Study

## 9.11.3.1 Safety Follow-up Visit

The mandatory Safety Follow-up Visit should be conducted approximately 30 days after the last dose of study treatment or before the initiation of a new anticancer treatment, whichever comes first. If a participant discontinues from the treatment period approximately 30 days or later after the last dose of study treatment a separate Safety Follow-up visit does not need to be completed. The End of Treatment/Discontinuation visit should be completed only and include any assessments required at the Safety Follow-up visit but not the discontinuation visit.

All AEs that occur prior to the Safety Follow-Up Visit should be recorded. Participants with an AE of Grade >1 will be followed until the resolution of the AE to Grade 0-1 or until the beginning of a new anticancer therapy, whichever occurs first. Serious AEs that occur within 90 days of the end of treatment or before initiation of a new anticancer treatment should also be followed and recorded.

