### 9.11.3.2 Disease Status Follow-up

Participants who discontinue study treatment for a reason other than disease progression per RECIST 1.1/iRECIST will move into the Follow-Up Phase and should be assessed as outlined in the SoA (Section 2) to monitor disease status. The Sponsor may request survival status to be assessed at additional time points during the course of the study (not to exceed approximately 12 weeks). Every effort should be made to collect information regarding disease status until the start of new anti-cancer therapy, disease progression, death, end of study. Information regarding post-study anticancer treatment will be collected if new treatment is initiated.

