#### 9.11.3.3 Survival Follow-up

Participants who experience confirmed disease progression or start a new anticancer therapy, will move into the Survival Follow-Up Phase and should be contacted by telephone approximately every 12 weeks to assess for survival status until death, withdrawal of consent, or the end of the trial, whichever occurs first.

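### SAEs are reportable to day 90, but no SAE enquiry is scheduled after the 30-day visit for participants who stop for confirmed progression and start no new therapy

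*Combined protocol and SAP*

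**What the plan says.** Section 9.3.1 of the protocol sets the reporting window for serious events: "All AEs meeting serious criteria, from the time of treatment allocation/randomization through 90 days following cessation of study treatment". The limit continues "or 30 days following cessation of study treatment if the participant initiates new anticancer therapy. whichever is earlier". Section 9.11.3.1 repeats the 90 days as a duty to follow and record, and sets the last safety visit: "The mandatory Safety Follow-up Visit should be conducted approximately 30 days after the last dose of study treatment". The SoA allows that visit a window of +7 days.

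The AE/SAE review row of the SoA (Section 2) is marked at screening, by an arrow from Cycle 1 Day 1 to Safety Follow-up, and under Imaging Follow-up. The Survival Follow-up cell is empty.

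What follows the safety visit depends on why treatment stopped:

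- Section 9.11.3.2: "Participants who discontinue study treatment for a reason other than disease progression per RECIST 1.1/iRECIST will move into the Follow-Up Phase". In the SoA this is the Imaging Follow-up column, which has AE/SAE review.
- Section 9.11.3.3: "Participants who experience confirmed disease progression or start a new anticancer therapy, will move into the Survival Follow-Up Phase". There they "should be contacted by telephone approximately every 12 weeks to assess for survival status". The SoA also marks subsequent antineoplastic therapy status in that column.

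Section 7.2.2 says of late toxicity: "These immune-related AEs (irAEs) may occur shortly after the first dose or several months after the last dose of pembrolizumab treatment".

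**The concern.** The reporting window and the visit schedule do not match for one group. A participant who stops for confirmed progression and starts no new anticancer therapy remains in the SAE window until day 90, yet the schedule gives the site no point after the safety visit at which to ask about SAEs. Section 9 makes adherence to the SoA a requirement, so sites can be expected to work from the empty cell.

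Two things are at stake. First, the unasked period is one in which the protocol itself expects immune-related events. Second, scheduled ascertainment depends on the reason for stopping, which arises after randomisation. If reasons for stopping were to differ between the 30 mg and 100 mg arms, late SAE summaries by arm would not be like for like. Safety is a primary objective (Section 4), Section 5.4.1.2 includes the incidence of SAEs among the safety endpoints, and Section 10.6.2 includes SAEs in the safety review.

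**Working it through.** The plan gives no figure of its own on this point, so the check sets the schedule against the window and then does the day arithmetic.

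**1. Who is affected.**

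| Reason for stopping | Phase after the safety visit | AE/SAE review in SoA | SAE window |
|---|---|---|---|
| Other than progression | Imaging Follow-up, every 12 weeks | Marked | To day 90 unless new therapy starts |
| Confirmed progression, new therapy by day 30 | Survival Follow-up | Empty | Closes at day 30, so no gap |
| Confirmed progression, new therapy after day 30 | Survival Follow-up | Empty | Shortened; 9.3.1 and 9.11.3.1 differ on where it ends |
| Confirmed progression, no new therapy | Survival Follow-up | Empty | To day 90: full gap |

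**2. Length of the gap**, in days after the last dose.

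- Safety visit at day 30: 90 − 30 = 60 days; 60/90 = 67% of the window.
- Safety visit at day 37 (+7): 90 − 37 = 53 days; 53/90 = 59%.
- Section 9.11.3.1 lets a discontinuation visit at about day 30 or later replace the safety visit. If that visit is later than day 37, the gap is shorter still.

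**3. Where the first survival call falls.** 12 weeks = 84 days, ±7 in the SoA. The starting point of the 12 weeks is not stated.

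- From the last dose: 84 ± 7 = days 77 to 91. A call on day 77 leaves 90 − 77 = 13 days of the window still to run.
- From a day-30 safety visit: 30 + 84 ± 7 = days 107 to 121, after the window has closed.

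Under either reading the SoA attaches no SAE review to the call.

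**4. Which analyses can change** (Sections 5.1.3, 10.4.2, 10.6.2).

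- DLTs are evaluated in Cycle 1. An SAE after treatment has ended cannot add one.
- Discontinuation due to an AE is already settled once treatment has stopped.
- Participants with at least one AE: a missed late SAE matters only if that participant has no other recorded AE.
- SAE, late immune-related and per-term AE summaries can change.

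**5. Illustrative size.** Every rate here is an assumption; the documents give none. Per arm of 60 (Section 10.9), participants with an unrecorded late SAE = 60 × g × s × m, where g is the share stopping for progression without new therapy before day 90 (20–60%), s the share of those with an SAE on days 31–90 (5–15%), and m the share of those missed (25–100%).

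- Low: 60 × 0.20 × 0.05 × 0.25 = 0.15 participants (0.25 percentage points).
- High: 60 × 0.60 × 0.15 × 1.00 = 5.4 participants (9 percentage points).

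For the count with at least one AE, multiply by the share with no other recorded AE (assumed 2–10%): 0.15 × 0.02 = 0.003 to 5.4 × 0.10 = 0.54 participants per arm.

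**The case against.** The best defence is that the duty to capture these events exists even though the cell is empty. Section 9.11.3.1 says SAEs within 90 days are to be followed and recorded. Section 9.3 makes investigators responsible for detecting events. Table 7 requires all SAEs to be reported through the follow-up period. Section 8.1 calls for data on clinical events after discontinuation to be collected to the last scheduled follow-up. Under 9.3.1 a drug-related SAE that comes to the investigator's notice is reportable at any time, which covers late immune-related SAEs if judged related. The survival call already asks about subsequent therapy, and no call script in the documents rules out an SAE question. Participants without progression also go unasked between the safety visit and their first 12-weekly contact, so the difference between the groups is one contact.

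Most of this stands as fact, and it rules out saying that events will be missed. It does not close the gap, because none of these provisions sets a contact for this group. The any-time rule is limited to drug-related SAEs that become known, whereas inside the window all SAEs are required. Section 9.3.2 prefers open verbal questioning of the participant, and none is scheduled. Section 9.3.1 also says investigators need not actively seek events in former participants; whether that includes people in survival follow-up is not stated.

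A reader might infer that the primary safety analysis will be under-counted and the dose comparison distorted. The documents do not support this. The Miettinen–Nurminen comparisons cover DLTs, participants with at least one AE, and discontinuation due to an AE. The first and third cannot change, and the second barely does. Nothing in the documents shows that reasons for stopping differ by dose.

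**Conclusion.** The mismatch holds. For participants who stop for confirmed progression and start no new anticancer therapy, capture of SAEs from about day 30 (day 37 at the latest if the safety visit is held within its window) to day 90 is passive. Late SAEs may be under-ascertained in this group, and ascertainment depends on why treatment stopped. The effect falls on SAE and late immune-related summaries by arm. It does not reach the DLT or discontinuation endpoints, and the effect on the at-least-one-AE count is negligible at most.

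The number of missed events cannot be computed from the documents; the range of 0.15 to 5.4 participants per arm only shows how strongly the answer depends on assumed rates. The size of the affected group is also unknown. The conclusion rests on the Survival Follow-up cell being intentionally blank and on sites following the SoA as written. The point is worth correcting because the repair is small, not because a primary result is at risk.

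**What to change.** In the SoA, mark AE/SAE review for the first Survival Follow-up contact. State that this contact is timed from the last dose and made at or just after day 90 for participants still in the SAE window. At that call, ask an open SAE question covering the whole interval since the Safety Follow-up visit. Marking the cell alone is not enough: without a stated starting point, the call may fall before day 90 or well after it.

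The cost is one SoA mark, one timing note, one added question on an existing call, and a few more SAE reports to process. In the same amendment it would help to align the wording of 9.3.1 and 9.11.3.1 on when the window ends after new therapy starts, and to state in Section 10.6.2 the day to which AEs and SAEs are counted, since none is given there.
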